University of Kansas Medical Center
RESEARCH PROTOCOL INVOLVING HUMAN SUBJECTS
TEMPLATE WITH GUIDANCE

Version date: 2/19/2024

Principal Investigator: [name]

Study Title: Added sugar intake and brain structure and function

Co- Investigator(s): [name]

I. Purpose, Background and Rationale

A. Aim and Hypotheses

1. The first 1000 days post-conception have been characterized as a critical window for brain development, during which much of the brain's growth, structure, and function is set¹. Key nutrients from maternal and infant dietary intake fuels these maturational processes, thus providing the potential underlying foundation for later cognitive development. Brain growth and development is particularly sensitive to poor nutrition during this window²; previous work detailed the effects of deficiencies in the status of folic acid, choline, iron, zinc, iodine, and long chain polyunsaturated fatty acids³. While nutrient deficiencies have been studied, less is known about the impact and timing of excess nutrition in relation to cognitive development⁴.

2. Aim 1: Determine the relationship between added sugars (% calories) intake during pregnancy and infancy/toddlerhood (birth to 24 months) on brain structure and function.
Hypothesis: added sugars intake will be negatively related to brain structure (hippocampal volume) and function (resting state functional connectivity and P3 amplitude). We will explore how sex modifies this relationship.

Aim 2: Determine the relationship between fructose (% calories) consumption during pregnancy and infancy/toddlerhood (birth to 24 months) on brain structure and function. Since some studies reported relationships with fructose independently, we will explore relationships with fructose separately.

Hypothesis: fructose intake will be negatively related to brain structure (hippocampal volume) and function (resting state functional connectivity and P3 amplitude). We will explore how sex modifies this relationship.

B. Background and Significance

1. Study Significance: Brain development is a protracted process that begins in early gestation and continues into late adolescence. By the 8th week in gestation, the basic brain structures and the central nervous system are formed, and neuron production and migration are started⁵. From the 8th week until delivery, the cortical and subcortical structures form, including the major fiber pathways. In the third trimester, myelination

and growth of the hippocampus increases rapidly until around 18-24 months of age¹. Rapid brain growth continues with a four-fold increase in brain size during early childhood, reaching 90% of full brain size by six years old. The first 1000 days post-conception have been characterized as a critical window for brain development, during which much of the brain's growth, structure, and function is set¹. During this time, the brain is particularly vulnerable to nutrient deficiencies, and such deficiencies can have a severe impact on cognitive development^{2,3}. Promoting optimal development and cognition has clear individual benefits, but also has substantial economic impact⁶⁻⁸. The prevention of later developmental deficits is estimated to save \$6B annually^{9,10}.

The concept that early development disproportionately affects later outcomes is widely accepted in the developmental sciences¹¹⁻¹⁵, and the nutrition literature¹⁶⁻²². Thus far, most research has focused on key early life nutrient deficiencies^{2,4,16}. Prenatal and postnatal long-chain polyunsaturated fatty acids (LCPUFA)²³ docosahexaenoic acid (DHA) and arachidonic acid (AA), iron²⁴⁻²⁷, and zinc²⁸⁻³⁰ promote brain structure development, myelination, neurogenesis, neuronal migration, synaptogenesis and production of neurotransmitters. Iron deficiency is related to decreased language skills and fine-motor skills^{31,32} and supplementing iron, copper, and zinc improved attention measures³³. Nutrient intake strongly supports the normal development of underlying neural structure and function that is critical for later cognitive development. While the effect of nutrient deficiencies is reported, the impact of excess nutrition is less studied.

2. The impact of excess nutrient intake on brain development and function has garnered far less consideration compared to nutrient deficiencies. Data suggest that added sugars intake during pregnancy, infancy, and toddlerhood may interfere with the early formation of the brain structures that contribute to learning and memory³⁴. Fructose is of particular interest here, as it is one of six monosaccharides represented in added sugars³⁵, and is found in the diet as a sweetener commonly added to foods during processing in the form of high fructose corn syrup (HFCS) and sucrose, a disaccharide made of a glucose bound to a fructose³⁶. HFCS is a low-cost sweetener commonly used in sugar sweetened beverages (SSB). The effect of fructose may be due to fructose metabolism not being tightly regulated like glucose metabolism³⁶ leading to oxidative stress and an inflammatory response³⁷.
3. Literature Review: The literature suggests that added sugars intake in early life exceeds recommendations. Added sugars are defined as sugars and syrups added as an ingredient to foods during processing, preparation, or at the table, while total sugars include added sugars plus sugar naturally occurring in foods (e.g., fruit and milk)³⁵. One added sugar in particular, fructose (e.g., high fructose corn syrup), has been investigated as a driver of the negative relationships reported between added sugars and health outcomes³⁸. Pregnant women are recommended to consume <10% of calories/day from added sugars, whereas infants and toddlers (<24 months) are recommended to consume no added sugars³⁹. Even so, pregnant women are reported to consume 15.8% of calories/day from added sugars⁴⁰, and 6- to 24-month-olds to consume 1.4-7.2% of calories/day from added sugars^{41,42}. Data in pregnant women and infants and toddlers

found 70% of pregnant women³⁹ and 97.3% of infants and toddlers consumed added sugars in each day⁴³. While this is concerning given the relationships between added sugars intake and chronic disease development⁴⁴⁻⁴⁶, evidence is growing that early added sugars intake is also related to diminished cognitive function⁴⁷.

In adolescent rodents and humans, added sugars (including fructose) negatively impacted the hippocampal structure and connectivity⁴⁸, increased hippocampal inflammation⁴⁹, and impaired hippocampal-dependent memory⁵⁰. Human data from the prenatal period and infancy are lacking, but one published study³⁴ found greater maternal prenatal consumption of added sugars was related to poorer cortical organization, and greater maternal fructose intake during lactation was related to lower scores in the offspring on the Bayley-III Scales of Infant Development at 24 months old⁵¹. These preliminary studies are consistent with the hypothesis that added sugars intake during pregnancy, infancy, and toddlerhood may interfere with the development and early formation of neural circuits³⁴, perhaps owing to increased oxidative stress/inflammation^{49,52,53} or decreased production of brain derived neurotrophic factor (supports brain development and circuit formation)^{52,54}, leading to suboptimal cognitive outcome. This hypothesis was further supported by preliminary data from our own laboratory, which found that added sugars intake during the first two years of life was related to lower scores on standardized cognitive tests from 18 months to 6 years of age. The purpose of this proposal is to understand the relationship between maternal and early offspring (birth to 24 months) added sugars intake and brain structure and function at 5-6 years of age.

In 7-11-year-old children⁴⁸, increased intake of fructose and glucose was associated with increased right hippocampal CA2/3 subfield volume, and increased fructose intake was associated with mean diffusivity in the right cingulate-prefrontal cortex connections. This suggests an impact on hippocampal structure related to an increase in hippocampal inflammation. In the Project Viva cohort⁵⁵, greater maternal prenatal intake of SSB was related to poorer offspring global intelligence. Greater maternal prenatal added sugars consumption was also related to lower newborn gray matter at 3 weeks old, including areas for later cognitive functioning³⁴, suggesting an impact on formation of dendrites and synapses. This cohort was tested again at 24 months using the Bayley-III Scales of Infant Development⁵⁶. Greater maternal SSB intake was related to lower scores on the Bayley-III. These data provide evidence for a relationship between maternal added sugars intake and the brain structures that are the foundation for future cognitive development.

C. Rationale

1. As described above, there is a growing body of evidence to suggest that excess added sugar intake negatively affects cognition.
2. The innovation for this proposal involves a shift with respect to the theoretical approach around the relationship between cognition and nutrition. *While the impact of key nutrient deficiencies on cognition is well documented, the relationship between excess intake (i.e., added sugars) and cognitive development has not been previously studied.* Further, data are lacking on exposure timing relative to the impact on cognition and brain

development. This proposal will investigate three time periods that are well established windows of brain development that are sensitive to nutrient exposures: the prenatal, infancy, and toddlerhood time periods.

3. n/a – this study is not designed to improve the diagnosis or treatment of a disease

II. Research Plan and Design

A. Study Objectives: This purpose of this study is to fill a gap in the literature by providing an understanding of the relationship between added sugars and fructose intake during sensitive windows to brain structure and function. This project is unique because we can determine the effect of added sugars during three different times: pregnancy, infancy, and toddlerhood.

Primary Aims:

Aim 1: Determine the relationship between added sugars (% calories) intake during pregnancy and infancy/toddlerhood (birth to 24 months) on brain structure and function.

Aim 2: Determine the relationship between fructose (% calories) consumption during pregnancy and infancy/toddlerhood (birth to 24 months) on brain structure and function.

Secondary Aims:

Secondary Aim 1: Determine the relationship between added sugars (% calories) intake during pregnancy and infancy/toddlerhood (birth to 24 months) on cognition.

B. Study Type and Design: This is a non-interventional, observational study.

Added sugar intake during pregnancy will be assessed using dietary data collected between 12-20 wks gestation using the National Cancer institute (NCI) DHQ-II food frequency questionnaire (FFQ) or three 24-hour dietary recalls.

Offspring dietary intake was collected at 2 weeks and at 6, 12, and 24 months by one multiple-pass 24-hour dietary recall administered to the child's caregiver and collected by trained research staff.

For the present study, we will collect three total dietary recalls: two weekday and one on the weekend.

Brain structure and function will be measured using MRI and EEG assessments. Cognition will be measured using dimensional change card sort task and Peabody picture vocabulary test.

C. Sample size, statistical methods, and power calculation

1. n/a – randomization will not be used
2. n/a – study will not be blinded
3. The present study is pilot. The planned sample size is 45 subjects.

D. Subject Criteria (See Vulnerable Populations appendix, if applicable): Participants who were previously enrolled in the ADORE GAINS study will be invited to participate in the present study when they are 5-6 years old. Participants will be both male and female and English or Spanish speaking.

1. Inclusion criteria: Participated in ADORE GAINS. Age 5-6.
2. Exclusion criteria: children who have received an autism diagnosis (per parent report)
3. Withdrawal/Termination criteria: n/a

4. Subjects may enter another research study while participating in this research study, as this study is observational only.

E. Specific methods and techniques used throughout the study

1. Laboratory tests: n/a
2. Study Procedures:

Dietary assessment: Three multiple-pass 24-hour dietary recall will be administered to the child/child's caregiver and collected by trained research staff to characterize energy and nutrient intake of the child. 24-hour recalls accurately estimate dietary intake^{57,58} and contain less reporting bias than diet records^{57,59}. The recalls are entered into the Nutrition Data System for Research (NDS-R, version 2021, Minneapolis, MN) for macro- and micronutrient analysis including added sugars.

Dimensional Change Card Sort (DCCS) task. This test is based on the basic paradigms of discrimination learning^{65,66}, which was a focus of our laboratory's research program during the 1990s^{67,68}. This particular task is administered according to the protocol published by⁶⁹, and has also been used in other nutritional studies, as well as in our research program on the development of attention in preschoolers⁷⁰. Essentially, participants are presented with stimuli that can be sorted on various dimensions (e.g., shape or color). They are asked to sort the stimuli on one dimension (thus providing a measure of performance on that ability) but then are asked to reverse (i.e., "switch") the rule. At that point, they must inhibit the previously activated rule in order to perform correctly under the new rules. For this particular task, children are presented a game in which they must sort 7 "red bunny" cards and 7 "blue car" cards into one of two boxes. One box is "labeled" with a red car and the other with a blue bunny. The child is asked to play either the "color game," with red bunnies sorted (face down) into the "red car" box; blue cars sorted (face down) into the "blue bunny" box; or they are asked to play the "shape game," with blue cars sorted (face down) into the "red car" box and red bunnies sorted (face down) into the "blue bunny" box. The protocol is to administer two practice trials, and then 6 trials with varying levels of support as needed (i.e., instructions may be repeated, or cards may be identified as a scaffold for the production of strategies) although the answers are never given to the child. If children perform 5 out of 6 trials correctly, the game is switched to the opposite (i.e., shape-to-color or color-to-shape). Should the child successfully negotiates the switch, the task would proceed with the "border version" of the task, where half of 12 sorting cards have a black border around the picture, and the child is asked to play "color game" when the card has a black border and "shape game" when it does not; here, there are 12 trials, but no game-switch phase. Correct responses are recorded for each phase, and performance is also qualitative characterized as 0 (fail pre-switch phase), 1 (pass pre-switch, fail post-switch), 2 (pass the pre- and post-switch phases, but fail border phase), and 3 (pass all phases). The DCCS task will take approximately 15 minutes.

Peabody Picture Vocabulary Test (PPVT). Receptive vocabulary will be assessed using the PPVT-4. The PPVT-4 is a nationally standardized assessment of receptive vocabulary that has been shown to be fair with respect to cultural and economic status⁷¹. In this task,

participants are shown pages depicting 4 pictorial choices. For each page, the examiner says a word, and the participant indicates, either by pointing or by stating a reference number, which picture best matches the word. Administration is simple and straightforward. The PPVT-4 yields a standard score normed with a mean of 100 and a standard deviation of fifteen. It takes about 30 minutes to complete.

If one or both cognitive tests (DCCS and PPVT) are not completed at the second study visit for any reason, such as subject fatigue, the study team can ask the family if they are willing to come back at a later date for completion of the test(s). Compensation of an additional \$50 would be provided if an additional visit is completed.

Dual energy x-ray absorptiometry (DXA) scan: (Prodigy, Madison, WI, encore software version 13.60) will be used to measure body composition and regional AT distribution. The DXA is located within the Dietetics & Nutrition Clinic inside the Smith West building at KUMC. Using specific anatomic landmarks as previously described, regions including the arms, legs and trunk will be demarcated⁷². Calculations for FM in each region and summed for regions comprising the central (trunk) and peripheral (arms plus legs) will be completed. If a child moves during the scan the scan may need to be re-done but no more than 2 scans will be given over the duration of the study. The DXA scan takes about 10 minutes.

If there is movement during the first DXA scan and the study team and/or parent does not think the child will lay still for a second scan, the family may be asked if they would come back a different day to complete a second DXA. As stated above, no more than 2 scans will be given over the duration of the study. Compensation of an additional \$50 would be provided if an additional visit to repeat the DXA scan is completed.

Anthropometry: Body weight will be assessed on a same calibrated scale (Detetco Scales, Webb City, MO). Standing height will be measured using a wall mounted stadiometer (Accu-Hite, Seca Corp, Hanover, MD). Subjects will remove shoes and be centered on the stadiometer. Height will be recorded to the nearest 0.1 cm. Two measurements will be taken and the average will be recorded. The measurements take about 5 minutes to complete.

Skinfolds: Six skinfolds will be measured to represent AT distribution in order to compare to larger trials that do not have DXA. [name] has published using these methods to assess infant FM distribution⁷³ and it has been argued skinfolds are a valid metric of regional FM⁷⁴. All measurements will be collected using standardized procedures to our Laboratory and will take place on the same day as the body composition assessment by DXA using standardized procedures. All skinfolds will be identified using anatomical landmarks and taken on the right side of the body using Lange calipers (Beta Technology, Santa Cruz, CA). Skinfolds will be taken in order from head to toe and then repeated in that same order. If two skinfold measurements differ by more than 1 mm, a third measurement will be taken. The two measurements within 1 mm will be averaged and used for analysis. Biceps and triceps skinfolds will be measured at the midline of the

anterior and posterior surface of the arm, respectively, on the mid-point between acromial process of the scapula and olecranon process of the ulna. Subscapular skinfold will be measured at the lower angle of the scapula. Suprailiac skinfold will be measured anteriorly to the midaxillary line and superiorly to the iliac crest, along the natural cleavage of the skin. The thigh skinfold will be measured at the mid-point between patella (kneecap) and inguinal crease at the anterior surface of the thigh. Flank skinfold will be measured immediately above the iliac crest at the mid-axillary line. Central FM will be calculated by adding the subscapular, suprailiac and flank skinfolds and dividing by two. Peripheral FM will be calculated by adding the thigh, biceps and triceps skinfolds and dividing by three. The skinfolds take about 15 minutes to complete.

If the anthropometric and/or skinfold measurements are not completed at the second study visit, for any reason, the study team can ask the family if they are willing to come back at a later date for completion of the measurements. Compensation of an additional \$50 would be provided if an additional visit is completed.

3. Measuring height and weight are part of usual care for this population. No other procedures are part of usual care. None of the tests or measurements will be billed to insurance.
4. n/a – no tissue samples will be collected
5. Timeline:

Procedure	Study Visit 2
Questionnaires	x
Diet Recall (3 total)	x
MRI acclimation scan	
MRI scan	
EEG	
Card sorting game	x
Picture vocabulary test	x
Anthropometry & skinfolds	x
DXA scan	x

F. Risk/benefit assessment: No appreciable risk of physical, psychological, social, legal or other harm is expected.

Physical risk: The DXA exposes the subject to a small amount of radiation during the scan. One DXA scan is equivalent to approximately 2 hours of natural background radiation. To minimize radiation exposure, no more than two DXA scans will be completed for this study. Subjects may feel a light pinch when calipers are used to measure skinfolds. Study staff will be adequately trained and use gentle techniques to minimize discomfort.

1. Psychological risk: Some children may get tired during the cognition tests and not perform at their best
2. Social risk: n/a
3. Economic risk: n/a

4. Potential benefit of participating in the study
 - a. n/a – no direct benefit to the individual subject or parent
 - b. n/a – no direct benefit to the population from which the subject is drawn
 - c. The information gained in this study will fill a gap in the literature by providing an understanding of the relationship between added sugar intake during a sensitive window of brain development. This data will help inform public health recommendations for added sugar intake and inform when interventions should occur.

G. Location where study will be performed: All study visits will occur at the KU Medical Center main campus in Kansas City, KS. The study visit will occur at [name] research laboratory in the SmithWest building. All participants will be assigned a non-identifiable subject number. Subjects' records will be stored electronically on the KUMC RedCap server. All paper records will be kept in [name] locked research laboratory. Only approved study team members have access to this area.

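### The plan says it can determine the effect of added sugars in pregnancy, infancy and toddlerhood separately, but its exposure definitions and unadjusted correlations cannot separate those windows

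*Combined protocol and SAP*

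**What the plan says.** Three places give the study a timing purpose.

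- I.C Rationale names timing as a gap in the literature ("data are lacking on exposure timing relative to the impact on cognition and brain") and continues: "This proposal will investigate three time periods that are well established windows of brain development".
- II.A Study Objectives: "This project is unique because we can determine the effect of added sugars during three different times: pregnancy, infancy, and toddlerhood".
- II.F Risk/benefit assessment: "This data will help inform public health recommendations for added sugar intake and inform when interventions should occur".

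The aims are worded differently. Aim 1, in I.A and again in II.A, reads: "Determine the relationship between added sugars (% calories) intake during pregnancy and infancy/toddlerhood (birth to 24 months) on brain structure and function". Aim 2 uses the same periods for fructose.

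On measurement, II.B says: "Offspring dietary intake was collected at 2 weeks and at 6, 12, and 24 months by one multiple-pass 24-hour dietary recall". Pregnancy intake comes from the "DHQ-II food frequency questionnaire (FFQ) or three 24-hour dietary recalls".

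On analysis, V.A.1 plans Pearson correlations for hippocampal volume and for connectivity, and correlations for the EEG amplitudes, with a Bonferroni correction. V.A.2 plans correlations for fructose. V.B lets the strength and significance of the correlations decide whether a relationship exists. II.C adds: "The present study is pilot. The planned sample size is 45 subjects".

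**The concern.** Saying that an effect can be determined at each of three times needs two things: a separate exposure for each time, and an analysis that distinguishes one time from another. The plan supplies neither. No section says which child recalls count as infancy and which as toddlerhood, or how they are combined. No section names a model containing more than one window, or a comparison between windows.

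What is at stake is interpretation. A correlation for one window could be reported as that window's effect when it partly or wholly reflects another. The timing statement in II.F would then rest on it. An unfixed rule for the recalls also leaves the child exposure in both primary aims open to choice after the data are seen.

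**Working it through.** **Is there a figure to reproduce?** No. The sample of 45 is stated without an alpha, power or effect size, so the check is textual, with an illustration of size.

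**Text side by side.** II.A names three windows. The aims name pregnancy and a slash-joined child period. II.B lists four single child recalls. Section V names correlations only. The public copy lacks some text between II.G and II.L, but the analysis text in section V reads on without a gap. The slash allows two readings.

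**Reading 1: child period pooled.** Let I and T be standardised infancy and toddlerhood intakes with correlation ρ, P = (I + T)/2, and Y a standardised outcome with coefficients b_I and b_T.

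- Covariance of P and Y = (b_I + b_T)(1 + ρ)/2.
- SD of P = √((1 + ρ)/2).
- Correlation of P and Y = (b_I + b_T)·√((1 + ρ)/2).

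Only the sum of the coefficients enters. With ρ = 0, the pairs (-0.4, 0), (0, -0.4) and (-0.2, -0.2) all give -0.4 × 0.707 = -0.283. No sample size can tell them apart.

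**Reading 2: child period split.** Suppose only window A is related to the outcome (true correlation -0.40) and window B is not, with between-window correlation ρ. The expected observed correlation for B is -0.40 × ρ × √(reliability of B). At ρ = 0.6 this is -0.24 without measurement error and -0.40 × 0.6 × √0.30 = -0.13 at reliability 0.30. It is zero only if ρ is zero.

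Inputs for the size:

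- n = 45 (II.C).
- Assumed: the true correlations, ρ, the reliabilities, base alpha 0.05 two-sided, and the number of tests. The documents give none of these.
- Single-recall reliability 0.30 (assumed). For the mean of three recalls: 3 × 0.30/(1 + 2 × 0.30) = 0.90/1.60 = 0.5625. Reliability of the food frequency questionnaire is not modelled.
- Bonferroni over six tests: 0.05/6 = 0.0083, about 0.8% per test.

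Share of studies (simulation, 40,000 runs) in which window B is significant, at ρ = 0.4 / 0.6:

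| Test level | No measurement error | Reliability 0.56 in A, 0.30 in B | Reliability 0.30 in A, 0.56 in B |
|---|---|---|---|
| Bonferroni, 3 tests | 8.8 / 21.1% | 3.6 / 6.1% | 5.5 / 11.1% |
| Bonferroni, 6 tests | 5.5 / 14.4% | 2.0 / 3.6% | 3.3 / 6.9% |
| Bonferroni, 12 tests | 3.4 / 9.7% | 1.1 / 2.0% | 1.9 / 4.3% |
| Uncorrected 0.05 | 18 / 36% | 9 / 14% | 12 / 22% |

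At ρ = 0.2 the uncorrected figures are 8%, 6% and 7%, against a nominal 5%.

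**Both windows in one model** (uncorrected 0.05, ρ = 0.4 to 0.6). Significance of window B falls from 18-36% to about 5% without measurement error, from 9-14% to 6-7% with reliability 0.56 in A and 0.30 in B, and from 12-22% to 9-14% with these reversed. Without measurement error, detection of window A falls from 79-80% to 60-72%.

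**The case against.** The strongest reply is that this is a labelled pilot whose aims speak of a relationship, not of separate effects. No aim promises to rank windows. The sentence in II.A is framing prose, and II.F says only that the data will help inform. All of that is fair, and it confines the point to those two statements and the missing exposure rule. Pilot status is a reason to soften the claim; it does not supply an analysis for it.

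Second, V.A.1 applies a Bonferroni correction. A reader might take the uncorrected 18-36% as the plan's error rate. The documents do not support that for Aim 1, since with six assumed tests the figure is 5.5-14.4%, and lower with measurement error. Bonferroni does not remove the carry-over, however: the rates still exceed the per-test level of 0.8%. The correction is stated under Aim 1 only.

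Third, the size rests on assumed inputs, and the reliability formula treats recalls at 2 weeks, 6 months and 12 months as interchangeable repeats of one quantity. This stands. The figures are illustrative.

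Fourth, a joint model in 45 children is imprecise. This also stands: it supports exploratory statements only, and is no reason to claim that window-specific effects can be determined after all.

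A reader might also infer that the problem will pass into the larger study mentioned in V.D. That section describes a funding resubmission to extend the study to the whole cohort. It does not say that this analysis or the timing claim would be reused, so the inference is not supported.

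**Conclusion.** The point holds as a mismatch between what II.A and II.F say about timing and what the aims and section V can deliver. That part needs no assumption: pooling cannot separate infancy from toddlerhood, and separate unadjusted correlations cannot attribute an association to one window when intakes are correlated.

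The practical size is uncertain. With six assumed tests and between-window correlation of 0.4 to 0.6, a window with no association of its own is significant in about 2% to 14% of studies, depending on measurement error, against 0.8% per test. It is a minor matter if intakes across windows are nearly uncorrelated. The planned correlations remain usable as unadjusted associations. The change should be made because it is cheap and the plan as written cannot support its stated property.

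**What to change.** 1. In II.A and II.F, describe timing as exploratory association, and remove the claim that window-specific effects can be determined.
2. In V.A, define the infancy and toddlerhood exposures in advance from the existing recalls, including their weighting. One example is the mean of the 2-week, 6-month and 12-month recalls for infancy and the 24-month recall for toddlerhood.
3. For hippocampal volume, add one exploratory regression with the windows entered together. Report coefficients and between-window differences with confidence intervals and the number of children used.
4. Keep the planned correlations, label them as unadjusted, and do not rank windows by r or p.

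Cost: text changes and a little more analysis, with no new data. The joint model detects the active window less often, leaves some carry-over from measurement error, and drops children who lack a recall. Intervals will be wide. With three windows and between-window correlation of 0.2 to 0.6, the 95% half-width for a difference between standardised coefficients is 0.44 to 0.64, wider than the assumed effect of 0.40. At 0.4 to 0.6, a test that the three windows are equal has 23-33% power without measurement error, and 6-17% with reliabilities 0.56, 0.56 and 0.30.
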